There are continued disparities in cancer incidence, mortality, and survival between American Indians (AIs) and Whites on cancers responsive to early screening (i.e., breast, colon-rectum [CR], and cervical) in the US. In New Mexico (NM), AIs compared with other racial/ethnic populations are significantly less likely to adhere to recommended screening guidelines. Differences in screening rates between AIs and Whites in NM range from a low of 11.5% (breast) to a high of 27.3% (CR)¹⁻⁴. There is an urgent need for testing culturally and linguistically targeted and theoretically guided interventions that support AIs in meeting the Healthy People 2020 targets for screen detectable cancers (breast: 81.1%; CR: 70.5%; cervix: 93.0%). Our long-term goal is to enhance health equity and reduce cancer disparities in morbidity, mortality, stage-at diagnosis, and survival among Zuni people through effective screening and prevention interventions. Our overall objective, which is the next step toward attainment of our long-term goal, is to develop a new participatory collaboration for cancer control research with the largest tribal community in NM (Zuni Pueblo) and the Indian Health Service (IHS) Zuni Comprehensive Health Center to conjointly build research capacity, assess cancer control needs of the Zuni people, identify strategies to enhance screening for the three screen detectable cancer (breast, CR, and cervix) per recommended guidelines, define cancer prevention and control priorities, develop a Zuni-specific cancer research plan and a model for cancer research among other AI tribes in rural NM, and develop and pilot test culturally and linguistically appropriate interventions to enhance age- and risk-appropriate breast, CR, and cervical cancer screening in concordance with the U.S. Preventive Services Task Force recommended guidelines. This research project is designed to use a formative, mixed-method approach to answer the research questions: “What are the cancer control needs and community-identified intervention strategies to control and prevent the three screen detectable cancers among the Zuni people”? And, “Does multi-directional and participatory cancer-related training, education, and cancer prevention and control intervention research enhance cancer health equity among the Zuni people?” The rationale for this study is that once we know the cancer control needs of the Zuni people and their preferences for the design of intervention programs for the three cancers, we can develop, implement and test the efficacy of targeted evidence based and theoretically informed cancer control and prevention interventions. [NOTE: At the request of the Zuni tribal leaders, we have included prostate cancer in the proposed formative research as the leaders would like to learn about their communities’ views regarding prostate cancer. There are no Community Guide recommendations or Health People 2020 targets for screening for prostate cancer.]

We plan to test our central hypothesis and, thereby, accomplish the overall objective by pursuing the following specific aims:

Aim 1: Develop a sustainable multi-directional, participatory collaboration (“community collaborative”) between the Zuni tribal leadership, Zuni stakeholders (i.e., Health and Wellness program directors and Community Health Representatives [CHRs], cancer survivors), IHS Zuni Comprehensive Health Center, Albuquerque Area Southwest Tribal Epidemiology Center (AASTEC), and the UNM Comprehensive Cancer Center (UNM CCC). We will establish a Tribal Advisory Panel (TAP) and community collaborative with representation from entities list here.

Aim 2: Empower and develop capacity (using the Freirean educational pedagogy for adult learning) among Zuni people to participate in relevant cancer control education and research.

Aim 2a: Train Zuni Community Health Representatives (CHRs) in qualitative research.

Aim 2b: Educate CHRs about cancers of the breast, CR, cervix, and prostate.

Aim 3: Assess cancer control needs of the Zuni people for the screen detectable cancers and prostate cancer, and resources available at the Indian Health Service (IHS) Zuni Comprehensive Health Center to provide screening services.

Aim 3a: Elicit and document (using the Multi-level Health Outcomes Framework [MHOF]) for cancers of the breast, CR, cervix, and prostate prevailing knowledge and beliefs; prevention an early detection practices; facilitators and barriers to risk reduction and screening practices; facilitators and barriers to accessing screening services; and, potential strategies/interventions to enhance cancer screening. We postulate that the qualitative methods will provide contextually rich data on what the Zuni people know about the screen detectable cancers and prostate cancer, what their beliefs are about these cancers, how their beliefs and cultural norms influence help-seeking behaviors, and what multi-level and multi-component strategies must we implement to enhance screening.

Aim 3b: Document resources available at the IHS Zuni Comprehensive Health Center. We postulate that the IHS Zuni Comprehensive Health Center will be under-resourced to provide screening services.

Aim 4: Evaluate the cancer-related knowledge, attitudes, and self-reported cancer-screening practices using quantitative survey methods among a convenience sample of Zuni people. We postulate that the survey will validate the information collected through the focus groups.

Aim 5: Integrate data to better understand cancer prevention and control challenges for the Zuni people:

- (a) Ascertain cancer burden, risk factors, and screening rates among the Zuni people.
- (b) Synthesize data collected as part of Aim 3b on resources available in the community, IHS Zuni Comprehensive Health Center, and at UNM CCC that can address the Advisory Panel-identified cancer prevention and control priorities.
- (c) Synthesize data collected as part of the qualitative and quantitative research (Aims 3a and 4).

Aim 6: Develop a cancer prevention and control research agenda for tribal communities in rural NM:

- (a) Develop a Zuni-specific comprehensive plan for research and evidence-based interventions in cancer prevention and control.
- (b) Design a model, based on the lessons learned, for a collaborative cancer prevention and control research agenda for tribal communities across rural NM.

Aim 7: Using participatory approaches by engaging the TAP, finalize multilevel/multicomponent intervention strategies to increase provider delivery of, community access to, and community demand for screening for the screen-detectable cancers.

Aim 8: Pilot test (using quantitative and qualitative methods) the multilevel/ multicomponent culturally and linguistically appropriate intervention strategies on outcomes such as: impact on screening practices; feasibility of implementation and acceptability of the intervention; and cost effectiveness of the intervention.

2. Background

Cancer epidemiology and screening rates. There are continued disparities in cancer incidence, mortality, and survival between AIs and Whites on cancers responsive to early screening (i.e., breast, colon-rectum [CR], and cervical) and prostate cancer in the United States (U.S.). For the period 1990-2009, based on data from Contract Health Service Delivery Area Counties across the U.S., the mortality-to-incidence ratios (indicator of survival) for these cancers were significantly higher for American Indian/Alaska Natives compared to Whites (breast: 1.22, CR: 1.16, cervix: 1.36, prostate: 1.40)⁵, indicating poorer survival. AIs in New Mexico also experience substantial cancer health disparities. For the period 2010-2014, AIs compared to Whites had higher incidence rates (per 100,000) for cervical (7.9 vs. 6.9) and CR (male: 46.5 vs. 35.2; female: 29.2 vs. 28.2) cancers, and higher mortality rates for cervical (3.7 vs. 1.3) and CR (males only; 18.9 vs. 15.6) cancers⁶. AIs were also more likely to receive a late-stage (i.e., regional or distant)

cancer diagnosis for all three screen detectable cancers⁷. AIs have some of the lowest cancer screening rates compared with other racial/ethnic groups. In New Mexico, AIs listed in the IHS Albuquerque Area have substantially lower screening rates than the state's White population do. AIs had screening rates of: breast (58.5%, women ages 52-64), CR (41.9%, ages 50-75), and cervical (63.9%, women ages 24-64) cancers¹; whereas, screening rates for Whites were: breast (70.0%, ages 50-74)⁴, CR (69.2%, ages 50-75)², and cervical (77.8%, women 21-65)³.

Barriers to screening. AIs experience substantial barriers when accessing and utilizing cancer-screening services. They hold varying cancer-related belief systems that influence the modalities of health care they seek. Tribes possess remarkably few health care resources to address cancer disparities where health care is significantly underfunded, services are often fragmented, and acute care needs take precedence over preventive health services⁸. Many IHS facilities have insufficient staff and high provider turnover, which results in abbreviated patient-provider encounters and insufficient communication⁸. Other documented barriers to cancer screening among AIs include cost/insurance, fear, stigma, transportation, embarrassment, trust, perceptions of discrimination, privacy issues, beliefs, knowledge about cancer screening, limited access to healthcare providers, lack of symptoms, and no screening recommendation made by providers⁹⁻¹⁸.

Summary of Significance. AIs experience substantial disparities in screen detectable cancer with higher incidence, disproportionate diagnosis of late stage disease, higher mortality, and poorer survival. Despite the documented efficacy of screening exams when used per recommended guidelines, AIs have lower screening rates; in part attributable to individual, social, and structural barriers. There is a paucity of data specific to Zuni people on their knowledge, attitudes, beliefs regarding cancer and cancer screening, and about potential strategies to enhance cancer screening. Therefore, the first necessary step is to document Zuni people's needs regarding screen detectable cancers. Future studies will utilize the results from this project to inform the development, implementation, and efficacy testing of intervention strategies that are tailored to the unique cancer control needs of the Zuni people and target the Zuni community.

Innovation

The proposed research is innovative, in our opinion, for the following reasons. First, it uses participatory research approaches^{19,20} to develop a "community collaborative" and to train Zuni CHRs for cancer control research and education. Second, it documents barriers and seeks solutions from Zuni community members towards the design of specifically tailored and targeted cancer prevention and control interventions, as recommended²¹⁻²⁴. Third, it uses a multi-level theory of behavior change²⁵⁻²⁷ to analyze formative data, along individual, environmental, contextual, social, and policy promoters and barriers²⁸ for behavior change. Fourth, it works collaboratively with a population that experiences acute health inequities to determine needs and intervention strategies. Fifth, it uses multiple methods (qualitative and quantitative, including constituency-involving processes) for data collection. These innovative steps will provide for the translation and implementation of more meaningful and realistic cancer prevention and control interventions that are applicable to "real world" settings by being responsive to community needs while acknowledging limitations of treatment-focused healthcare services, challenges to local healthcare access, and the exigencies of limited healthcare resources.

3. Study Design

Preliminary Work. [name] has conducted community-engaged descriptive and evaluative health disparities research using mixed methods (including quantitative surveys, and qualitative focus groups and semi-structured interviews) with a special emphasis on breast, CR, and cervical cancer screening^{22,23,29-31}.

General Overview. We will conduct the study in the Zuni Pueblo, in community-based settings and in the IHS Zuni Comprehensive Health Center. We will develop capacity among Zuni CHRs for cancer education

and research (Aim 1). Next, we will use a qualitative design featuring focus groups with community members and focus groups or interviews with healthcare providers (Aim 2). This formative work will enable us to learn about the range of factors that influence cancer screening and potential strategies to enhance it. Lastly, we will validate the qualitative findings using a quantitative design featuring a population-based survey of community members (Aim 3).

Research Setting. The Pueblo of Zuni is the largest tribal community in NM. The main Zuni reservation is located in McKinley and Cibola counties in the western part of NM. Based on the non-metropolitan 2013 Rural-Urban Continuum Codes (RUCC), these counties are in category 5. The Zuni Pueblo is a small rural community (~11000 residents), 97% of whom are American Indian³². Nearly 90% of the residents of Zuni speak a language other than English (i.e. the Zuni language—"Ashiwi awan benawe") at home³². The population is relatively young (median age, 33.2 years) and 72.4% are high school graduates or higher. More than one-third (37.5%) live below the poverty level, with a median household income of about \$38,000³².

Theoretical Framework. The Multi-level Health Outcomes Framework (MHOF) is a conceptual model to guide descriptive and intervention research in cancer prevention and control²⁵⁻²⁷. The MHOF is a synthesis of several conceptual formulations in the area of health behavior and outcomes and takes a multi-level (socio-ecological) perspective. The MHOF is a critical asset as it provides a framework for systematically analyzing the descriptive data collected for the proposed study. The MHOF has been applied and tested in a wide range of studies involving multiple racial and ethnic groups, disease targets, and intervention types and has been shown to be robust^{22,26,27}.

[figure not shown]
Community-Based Participatory Research (CBPR).

This approach effectively addresses mistrust of research and researchers through establishing a non-hierarchical partnership model^{19,20}. CBPR is used successfully to address a variety of health priorities^{19,20} and is a necessary research methodology with AIs³³⁻³⁶. We will constitute an Advisory Panel comprising stakeholders representing Zuni community members and CHRs, cancer survivors, IHS healthcare providers, and researchers. The Panel will actively participate in the research, including finalization of the study aims, research design and approach, recruitment strategies, development of data collection instruments, and constituency checking of data inferences. We will (1) build on the various stakeholders' strengths, and integrate our respective knowledge and expertise and (2) support an inter-dependent partnership, with a long-term commitment for mutually beneficial co-learning and capacity enhancement. The Panel will comprise nine members and will meet every six months or more often if necessitated. Panel members will receive \$100 for their participation and contributions.

4. Inclusion and Exclusion Criteria

- 4.1. People will be screened for eligibility for the respective sub-projects (Aims 3, 4, 7, and 8) by trained staff. Participants who meet the inclusion criteria for the sub-projects, as defined below according to self-report on the screening form, will be invited to participate in the respective part of the study.

4.2. Inclusion Criteria for Aim 3 – AI Female Aged 50-75 Year Focus Groups

4.2.1. *Criteria for Focus Groups on Cancers of the Breast, Colon-Rectum, and Cervix:*

4.2.1.1. AI woman aged 50-75 years old

4.3. Inclusion Criteria for Aim 3 – AI Male Aged 50-75 Year Focus Groups

4.3.1. *Criteria for Focus Groups on Cancers of the Colon-Rectum and Prostate:*

4.3.1.1. AI man aged 50-75 years old

4.4. Inclusion Criteria for Aim 3 – AI Female Aged 21-49 Year Focus Groups

4.4.1. *Criteria for Focus Groups on Cancer of the Cervix:*

4.4.1.1. AI woman aged 21-49 years old

4.5. Inclusion Criteria for Aim 3 – Tribal Advisory Panel (TAP) member Focus Group

4.5.1. Member of the Tribal Advisory Panel

4.6. Inclusion Criteria for Aim 3 – Healthcare Provider Focus Group

4.6.1. Provide healthcare within the IHS Zuni Comprehensive Health Center

4.7. Inclusion Criteria for Aim 4 – AI Male and Female Surveys (see “EligibilityScreener_Survey_2020_06_22_V1”)

4.7.1. *Cervical Cancer Survey:* AI women 21-49 years old and residing in the Zuni Pueblo

4.7.2. *Colorectal, Breast, and Cervical Cancer Survey:* AI women 50-75 years old and residing in the Zuni Pueblo

4.7.3. *Colorectal and Prostate Cancer Survey:* AI men 50-75 years old and residing in the Zuni Pueblo

4.8. Inclusion Criteria for Aim 7 – Development of the Interventions (Focus Groups to Develop Small Media)

4.8.1. AI man aged 50-75 years old

4.8.2. AI woman aged 21-75 years old

4.9. Inclusion Criteria for Aim 8 – Pilot Testing of the Interventions

4.9.1. For the Breast Cancer Intervention: AI women age 50-75, average risk for breast cancer, and never had a mammogram OR not had a mammogram within the past 2 years.

4.9.2. For the Colorectal Cancer Intervention: AI men and women aged 45-75, average risk for CR cancer, and never had a fecal occult blood test (FOBT), or fecal immunochemical test (FIT) or a colonoscopy OR not had a FOBT or FIT in the past year, OR no colonoscopy in the past 10 years.

4.9.3. For the Cervical Cancer Intervention: women aged 21-75, never had a cytology (Pap smear) OR had a Pap smear more than 3 years ago OR women aged 30-75, and never had screening with a combination of cytology and human papillomavirus testing OR no combination of testing in the past 5 years.

4.10. **Exclusion Criteria**

- 4.10.1. Cognitively impaired adults are excluded from participation
- 4.10.2. Adults not able to consent for themselves are excluded from participation
- 4.10.3. Prisoners may not participate in this study

5. Number of Subjects

5.1. Aim 3

- 5.1.1. Aim 3 is formative and therefore the sample size is not guided by a power analysis. For each of the up to 21 focus groups (until we reach thematic saturation), N=12-15 eligible persons will be invited, with the expectation that on average N=8-12 will attend. Since this is a community-based participatory study, we will not turn away any eligible person who show up for the focus group. Thus, we seek approval for including 150 AI men and women for the focus group.
 - 5.1.1.1. *Focus Groups Among Women aged 50-75 on Cancers of Breast, Colon-Rectum, and Cervix*: up to 5 Focus Groups, or until we reach thematic saturation (participants: N=60-75)
 - 5.1.1.2. *Focus Groups Among Men aged 50-75 on Cancers of the Colon-Rectum and Prostate*: up to 5 Focus Groups, or until we reach thematic saturation (participants: N=60-75)
 - 5.1.1.3. *Focus Groups Among Women aged 21-49 on Cervical Cancer*: up to 5 Focus Groups, or until we reach thematic saturation (participants: N=60-75)
 - 5.1.1.4. *Focus groups with Tribal Advisory Panel (TAP) members*: up to 3 Focus Groups, or until we reach thematic saturation (participants: N=36-45- total)
 - 5.1.1.5. *Healthcare Provider focus groups*: up to 3 Focus Groups, or until we reach thematic saturation (participants: N=36-45 total)

5.2. Aim 4

- 5.2.1. Aim 4 is to conduct surveys with approximately N=250-280 eligible AI men and women.
 - 5.2.1.1. *Survey on Cancer of the Cervix (Women aged 21-49)*: N=50-60 AI women
 - 5.2.1.2. *Survey on Cancers of the Colon-Rectum, Breast, and Cervix (Women aged 50-75)*: N=100-110 AI women
 - 5.2.1.3. *Survey on Cancers of the Colon-Rectum and Prostate (Men aged 50-75)*: N=100-110 AI men

5.3. Aim 7

- 5.3.1. Aim 7 is to develop the interventions, including the small media, with about 12-15 TAP members (section 4.5) and 150 eligible AI men and women (we will invite 12-15 participants

in up to 15 total focus groups, with expectation that on average we will have 8-10 participants will attend) (section 4.8)

5.4. Aim 8

5.4.1. Aim 8 is to test the three interventions with about up to 150 eligible participants

Total between the Aims: N=706-850 participants

6. Study Timelines

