We will conduct focus groups³⁸ with purposively sampled eligible participants. Eligible participants will include those who are not compliant with U.S. Preventive Services Task Force screening guidelines for the three cancers³⁹⁻⁴¹ and those who are eligible for prostate cancer screening. For breast cancer this would include AI women aged 50 to 74 at average risk for breast cancer who have never had a mammogram or have not had a mammogram within the past two years. For CR cancer, this would include men and women at average risk for CR cancer aged 50 to 74 and never had a fecal occult blood test (FOBT) or fecal immunochemical test (FIT) or a colonoscopy, or not had a FOBT or FIT test in the past year, or no colonoscopic exam in the past 10 years. For cervical cancer this would include women at average risk for cervical cancer aged 21 to 65 who have never had a cytology (Pap smear) or had a Pap smear more than 3 years ago; or women aged 30 to 65 who have never had screening with a combination of cytology and human papillomavirus (HPV) testing or no combination testing in the past five years. For prostate cancer, this would include men over the age of 50 years.

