13.1. The patient questionnaires will be analyzed utilizing approaches consistent with each data source. The structured questions will be exported from REDCap to a statistical software package for analysis. The qualitative responses to the questionnaire will be digitally recorded and transcribed for standard content analysis. The UNMCCC's Behavioral Measurement and Population Science Shared Resource will support the qualitative and quantitative data analysis efforts.

13.2. Quantitative Data Analysis (Aims 4 and 8): We will use descriptive statistics to characterize participant characteristics and their knowledge, attitude, screening practices, and preferred intervention strategy. We will use univariable and multivariable logistic regression analyses, with inclusion of modeling variables informed by the MHOF, to assess the relationship between socio-demographic variables, knowledge, and attitudes and beliefs on screening behaviors (Aim 4).

For Aim 8, for the primary outcome (completion of cancer screening), we will compare the number of cancer screening approaches (i.e., screenings for breast, CR, and/or cervical cancers) undertaken by study participants (based on age and gender), offset by the number of possible screening tests, using Poisson regression approaches between those who are and are not receiving active intervention. This will enable the estimation and comparison of screening uptake between treatment arms, even when there are different numbers of possible screening tests for groups of participants. We will account for within-cluster correlations using generalized estimating equations, and we will explore the impact on screening uptake of patient characteristics (e.g. sex) using fixed effects.

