4, the study utilized a contact sheet (ContactSheet_2021_01_07_V2) that asked participants if they would like to be contacted for future research. As part of Aim 8's recruitment, we will follow-up with these previous participants that consented to being contacted to assess interest and eligibility for the intervention in addition to recruitment via flyers. We will provide potential participants a description of the study (StudyDescription_Intervention_2022_10_26_V1) and review eligibility criteria (Eligibility Screener_Intervention_2023_02_02_V2). If the person is eligible and interested in participating in the survey, we will collect information (ContactSheet_Intervention_2022_10_26_V1) to enable us to contact the participant for the study activities. This contact information will be kept separate from the baseline survey. To mitigate COVID-10 risks, the study would also be able to mail the merchandise cards via US Postal Service to participants using the mailing address on contact sheet. The contact sheet for the intervention (ContactSheet_Intervention_2022_10_26_V1) includes a question on whether participants would like to be contacted for future studies. For those participants that agree to be contacted, these participants will form our recruitment pool for the Aim 8 qualitative focus groups and interviews.

21. Provisions to Protect the Privacy Interests of Subjects

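### As written, 4.9.2 and 4.9.3 admit to Aim 8 people already current by one colorectal or cervical test, and 13.2 does not say how baseline screening status or test dates enter the primary outcome

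*Combined protocol and SAP*

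**What the plan says.** - **Colorectal (4.9.2).** Men and women aged 45–75 at average risk qualify if they have never been tested, "OR not had a FOBT or FIT in the past year, OR no colonoscopy in the past 10 years".
- **Cervical (4.9.3).** A cytology branch covers ages 21–75. Joined to it by OR is a second branch for ages 30–75: "never had screening with a combination of cytology and human papillomavirus testing OR no combination of testing in the past 5 years".
- **Exclusions (4.10).** These cover cognitive impairment, inability to consent and prisoners. Nobody is excluded for being up to date.
- **How eligibility is applied (4.1).** It is decided "according to self-report on the screening form". Section 12 names an Aim 8 screener, but its content is not in the documents.
- **The parallel list (section 12, Aim 3).** Nearly the same OR conditions, with somewhat different age limits, follow this sentence: "Eligible participants will include those who are not compliant with U.S. Preventive Services Task Force screening guidelines". The Aim 8 text has no such sentence.
- **Recruitment (20.1).** For Aim 8, besides flyers, the team writes of Aim 4 respondents that "we will follow-up with these previous participants that consented to being contacted to assess interest and eligibility for the intervention". The Aim 4 criteria do not ask about screening; 4.7.3, for example, reads "AI men 50-75 years old and residing in the Zuni Pueblo".
- **Analysis (13.2).** The Aim 8 primary outcome is a count of "screenings for breast, CR, and/or cervical cancers" that are "undertaken by study participants (based on age and gender"), offset by the number of possible tests, in a Poisson model with generalized estimating equations. Patient characteristics may be explored as fixed effects, with sex as the only example. No counting window is given, and no rule on baseline screening status.

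**The concern.** Each OR branch is sufficient alone. A man with a colonoscopy two years ago meets 4.9.2 because he has had no stool test in the past year. A woman of 40 with a Pap smear last year meets 4.9.3 if she has never had combination testing. Neither need be overdue in the sense that the Aim 3 procedures describe.

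The analysis section does not settle what happens to such people. Taken at face value, a person counts toward the offset by age and gender, whether or not a test was due, and a test counts toward the numerator whenever it was done. What is at stake is the meaning of the primary outcome: uptake among people who needed screening, or a mixture that includes people who did not.

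**Working it through.** **Step 1. Code the criteria as written.** The inputs are the intervals in 4.9.2 and 4.9.3. *Current* means done within the interval the text itself gives. The cervical rows take the latest Pap smear and apply the age-30 limit to the whole second branch.

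| Person | Current by at least one listed test? | Passes 4.9 as written? |
|---|---|---|
| Colorectal: neither test current | No | Yes |
| Colorectal: colonoscopy 3 years ago, no stool test in past year | Yes | Yes |
| Colorectal: stool test 6 months ago, no colonoscopy in 10 years | Yes | Yes |
| Colorectal: both current | Yes | No |
| Cervical, age 40: Pap 1 year ago, never combination-tested | Yes | Yes |
| Cervical, age 40: combination test 4 years ago, no later Pap | Yes | Yes |
| Cervical, age 40: Pap 1 year ago, combination test 4 years ago | Yes | No |
| Cervical, age 25: Pap 1 year ago | Yes | No |

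The written rule turns away only people current on both kinds of test. There is one further looseness. The cytology branch refers to a Pap smear more than 3 years ago without saying the most recent one. Read just as literally, it also admits a woman of any eligible age, including 21–29, who has both an old and a recent Pap smear. The breast criterion (4.9.1) has one test and one interval and is not affected.

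**Step 2. Look for a correction elsewhere.** 4.10 supplies none. The Aim 8 procedures in section 12 add no requirement to be overdue. The Aim 4 pool was chosen without regard to screening status. Any filtering therefore rests on the screener.

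**Step 3. See whether the offset is defined.** Section 12 plans 60 men aged 45–75, 60 women aged 45–75 and 30 women aged 21–44; 60 + 60 + 30 = 150, matching 5.4.1.

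- Counted by cancer, possible screenings total 60×1 + 60×2 + 30×1 = 210 to 60×1 + 60×3 + 30×1 = 270.
- Counted by test, assuming two colorectal tests, one breast test, and one cervical test under age 30 or two from age 30, they total 60×2 + 60×4 + 30×1 = 390 to 60×2 + 60×5 + 30×2 = 480.

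The numerator is worded by cancer and the offset by test. It is not stated whether *possible* means open by age and gender or the cancers for which the person qualified (compare 23.3).

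**Step 4. Direction of the effect.** Let f be the share already current at entry and u the uptake among the overdue. Assume that current people have no new test.

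- Only new tests count: recorded uptake = (1 − f)u.
- Earlier tests count: recorded uptake = f + (1 − f)u.

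The documents give neither f nor u for Aim 8, so all inputs here are assumed:

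| f | u = 20%, new only | u = 20%, earlier counted | u = 40%, new only | u = 40%, earlier counted |
|---|---|---|---|---|
| 0% | 20% | 20% | 40% | 40% |
| 20% | 16% | 36% | 32% | 52% |
| 40% | 12% | 52% | 24% | 64% |

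For a comparison of two groups with the same f, counting only new tests leaves u1/u0 unchanged but shrinks the difference to (1 − f)(u1 − u0) and costs precision. Counting earlier tests gives [f + (1 − f)u1]/[f + (1 − f)u0], which is nearer to 1 than u1/u0. This is not put into numbers, because the Aim 8 procedures describe no untreated group.

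**The case against.** The strongest reply is that the problem may exist only on paper. Eligibility is applied through a form that the documents do not contain, and that form may already require a person to be overdue by every listed test. Re-contacted Aim 4 respondents are also assessed for eligibility, so the unfiltered pool alone shows little. This stands: a reader might infer that up-to-date people were enrolled, and the documents do not show it.

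Second, new screening is the natural reading of 13.2, which speaks of tests undertaken and of uptake. The reminders in section 12 come after the session and stop once a person reports completing the exam. This also stands. A reader might infer that the plan counts tests done before entry; it does not say so, and the likelier consequence is lower absolute uptake and less precision. The window is still unwritten. Nor can its end be taken from the follow-up time, which is 12 months in 6.4.1 and 7 but 6–8 months in section 12.

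Third, a baseline survey is collected and the list of patient characteristics is open, so baseline status could be used. The accurate statement is that its use is not specified, not that it is ruled out.

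Fourth, a reader might infer a biased intervention effect of a particular size. That needs two groups with known shares of current people. 13.2 mentions a comparison, but the Aim 8 procedures describe no untreated group and no allocation.

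Fifth, a reader might think that the focus groups sort people by being up to date and so misclassify those current at entry. Section 12 says that adherent and non-adherent people will be combined, so that inference fails.

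**Conclusion.** The concern holds as a defect in the written criteria and a gap in the analysis text. As worded, 4.9.2 and the combination-testing branch of 4.9.3 admit people current by one test, and the cytology wording may admit others. Comparison with the Aim 3 procedures suggests that this was not intended. Because 13.2 states neither the use of baseline status nor a counting window, such people can enter both numerator and offset.

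Under the more natural reading they lower absolute uptake and cost precision. If earlier tests count, they raise uptake and, with equal shares in the groups, pull any comparison toward no effect. The size cannot be fixed from the documents; the percentages above rest on assumed values of f and u. If the screener already applies a stricter rule, the eligibility part becomes a correction of the text only, and the gap in 13.2 remains.

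**What to change.** 1. **Eligibility.** Reconcile 4.9.2 and 4.9.3 with the Aim 3 description in section 12 and with the screener actually used. The investigators should state the rule they mean, including whether the cytology branch refers to the most recent Pap smear. Report the rule that was applied to those already enrolled.
2. **Analysis.** In 13.2, include in numerator and offset only the cancers for which a participant was overdue at baseline under that rule, taken from screener or baseline survey answers. Count only tests done after baseline and up to the follow-up survey, and state when that survey falls. Show the all-enrolled result alongside, and report how many people cannot be classified.
3. **Timing.** Set this in a dated amendment before screening outcomes are examined, or label it post hoc. Section 12 reports low focus-group interest from the post-intervention survey, so some follow-up answers are already in hand.

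**Cost.** A few words in 4.9, a short paragraph in 13.2, and a smaller analysis set if current people were enrolled. For the 60 planned men, assumed values of f = 20% and 40% leave 60×0.8 = 48 and 60×0.6 = 36. With an assumed uptake of 20%, the 95% half-width 1.96√(0.2×0.8/n) goes from 10.1 percentage points at n = 60 to 11.3 at 48 and 13.1 at 36. The restriction also depends on test-specific answers in forms that are not in the documents.
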